4 STUDY DESIGN

4.1 Treatment Design

This will be a multicenter, open trial of oral letrozole versus combination of oral letrozole and clomiphene citrate for the treatment of infertility in patients with oligo-ovulation or anovulation. Patients will be randomized to one of two treatment arms, to receive either an initial dose of letrozole 2.5 mg alone or clomiphene citrate 50 mg and letrozole 2.5 mg for 5 days during their menstrual cycle. Letrozole dosing will be escalated in a stair-step fashion based on ovulation results. Max dose of letrozole will not exceed 7.5 mg.

Participation in active treatment will last for up to 3 treatment cycles, approximately up to 15 weeks. Participants will be monitored at monthly intervals during expected mid-luteal phase to evaluate response to medication by evaluating ultrasound and progesterone parameters.

The dose will be adjusted according to response at mid-luteal visit.

- Anovulatory progesterone level < 3 and no evidence of follicular development and corpora lutea → increase letrozole dose on that day. This would be considered start of new treatment cycle (CD3).
- Anovulatory progesterone level < 3 with evidence of follicular development (follicle ≥14 mm) → repeat progesterone level based on LH testing (6-8 days following positive) or at 2 weeks if no positive → increase dose at menses visit (2nd progesterone is ovulatory) or increase dose at time of second progesterone if level < 3.

- Progesterone level ≥3 → maintain same dose for next treatment cycle

Anytime ovulation induction medication is started, pregnancy test to be performed prior to initiation of new treatment cycle.

Randomization will be stratified by site, age (< 35 versus \geq 35) and BMI (< 30 and \geq 30) to ensure similar comparison groups in these characteristics that highly impact outcomes. Randomization will be via a computer based central randomization to ensure adequate allocation concealment.

Enrollment will take approximately 20 months if ~ 10 subjects are enrolled per month. Active subject participation will be through completion of 3 cycles. We will follow up with patient regarding pregnancy and delivery outcomes.

As previously mentioned, this is an open trial. Patient will be aware of the treatment intervention they are receiving. Currently, letrozole is considered the current standard of care/first line agent for WHO class II anovulation (women with PCOS). Both groups will be receiving at minimum the current standard of care treatment.

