3.2 Secondary Research Hypothesis and outcome measures

We will analyze secondary outcomes however due to sample size will not be able to power differences in pregnancy rate and live birth rate. Descriptive secondary outcomes will include positive pregnancy test, clinical pregnancy, and ongoing pregnancy. We will also evaluate number of corpora lutea determined by ultrasound, endometrial thickness and pattern by ultrasound. We will also monitor adverse events during treatment and side effect profile of both treatment arms.

We will evaluate pregnancy outcomes and report any fetal anomalies.

- 1. The combination treatment will result in higher live birth rate
 - a. Outcome measurement: live birth rate

- 2. The shortest time to pregnancy will be with the combination treatment.
 - a. Outcome measurement: time to pregnancy
- 3. Treatment with the combination will have a similar singleton pregnancy rate compared to treatment with letrozole.
 - a. Outcome measurement: Singleton pregnancy and singleton pregnancy rate; singleton pregnancy is defined as presence of single intrauterine gestational sac with a single fetal pole and observable heart motion. Multiple pregnancy rate will also be compared.
- 4. Treatment with the combination will have a similar pregnancy loss rate compared to treatment with letrozole.
 - Outcome measurements: Pregnancy loss (defined as spontaneous abortion occurring before 13 weeks gestation), biochemical (positive hCG test with spontaneously dropping hCG levels), ectopic pregnancy or pregnancy of unknown location
- 5. Side effect profile will be similar between both treatment groups.
 - a. Outcome measurements: # of days of reported side effects and acceptability of side effects.
- 6. Endometrial thickness and corpora lutea number will be similar between the two groups.
 - a. Outcome measurement: Endometrial thickness and corpora luteal number on CD21-23 transvaginal ultrasound or approximately 6-8 days following detection of LH surge. These outcomes will also be evaluated based on dosing.

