5.5.1 Randomization Procedures

Participants will be randomized using randomization tables generated by a statistician and uploaded to the project in RedCap. The randomization scheme will not be accessible to study staff in order to maintain allocation concealment. Study staff will randomize subjects by entering BMI category (<30 or 30+), age category (<35 or 35+) and site on the RedCap Randomization page. Once these fields are entered and confirmed to be accurate, staff will click the "Randomize" button under treatment group to receive the participants assigned treatment."

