6.2 Administration of Study Product

University of Iowa Study Team will deliver medication to satellite recruiting clinics.

The medication will be dispensed to the patient by one of Study Team members. Verification of correct tablet number, correct packaging and expiration date will be performed prior to dispensing.

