7.3 Intermediate Visits

Participants will return for a midluteal study visit on cycle day 21-24 or 7-9 days following positive ovulation prediction test to determine if ovulation occurred. This visit will include an ultrasound and a progesterone lab.

If there is no ovulation, the daily dose of letrozole will be increased by 2.5 mg, to begin immediately. During the first cycle after letrozole dose increase, participants would receive 5mg daily for 5 days. If participants receive a second letrozole dose increase, they would receive 7.5 mg Letrozole daily for 5 days. The maximum dose for Letrozole in this study is 7.5 mg. CC 50 mg will be given on the same days as the letrozole in all cycles in the combination arm. Midluteal visits will be performed in all cycles. Each participant will complete a maximum of 3 cycles of medical therapy. On average we expect this to be about 4 months time, however, delayed ovulation, a biochemical pregnancy, or 1st trimester pregnancy loss in the first or second treatment cycle could delay the start of subsequent cycles, and therefore would extend active participation.

Cycle 1 Midluteal Visit

Timing will be based on LH testing, ideally around 7-8 days post-positive test or CD21-24 if no positive test

- Transvaginal ultrasound to assess for corpora lutea and endometrial thickness and pattern
- Serum progesterone assessment for ovulation
- Review subject calendar log and record adverse events as reported by subject or observed by investigator.
- Determine dosage for next cycle based on ultrasound and progesterone results and record in RedCap
 - If there is no ovulation, the daily dose of letrozole will be increased by 2.5 mg (5mg). The combination arm will continue to receive CC 50mg along with the increased letrozole dose.
 - If there is ovulation, treatment will be repeated in the next cycle with the same dose of letrozole. The combination arm will continue to receive CC 50mg along with letrozole 2.5mg.
- Schedule a follow up Progesterone lab if necessary
 - Participants with anovulatory progesterone levels (<3 ng/ml) and evidence of follicular development will return for a repeat progesterone level assessment in 10-14 days.
 - Participants with elevated anovulatory progesterone levels (1.5 < P4 < 3.0) and corpus luteum on ultrasound will return for a repeat progesterone level assessment in 2-3 days

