12.3.5 Sample size calculation

Considering midluteal endometrial thickness previously reported in ovulatory letrozole treatment cycles and hypothesized ovulation rates, the planned sample of 184 patients will have 94% power to detect a .25mm difference in midluteal endometrial thickness between the two arms among patients who ovulate. Assuming follicles >15mm on CD 12-14 in our preliminary study are indicative of corpora lutea, the planned sample will have 90% power to detect a 0.3 difference in mean number of corpora lutea among patients who ovulate.

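### No masking of the mid-luteal scan is described, although the scan supplies secondary outcomes and decides who is retested; the primary outcome is largely protected

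*Combined protocol and SAP*

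**What the plan says.** Section 4.1 describes "This will be a multicenter, open trial of oral letrozole versus combination of oral letrozole and clomiphene citrate" and adds: "As previously mentioned, this is an open trial. Patient will be aware of the treatment intervention they are receiving". The only protection described is concealment of the allocation sequence before assignment (5.5.1): "The randomization scheme will not be accessible to study staff in order to maintain allocation concealment". After assignment, section 6.2 says "The medication will be dispensed to the patient by one of Study Team members", and section 6.1.1 gives the combination arm a second, separately labelled vial.

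The mid-luteal scan has two uses.

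- **It supplies secondary outcomes.** Section 3.2: "We will also evaluate number of corpora lutea determined by ultrasound, endometrial thickness and pattern by ultrasound". Item 6 of that section predicts that thickness and corpora lutea number will be similar between the arms; it makes no prediction for pattern. Section 7.3 schedules the scan in each cycle: "Transvaginal ultrasound to assess for corpora lutea and endometrial thickness and pattern".
- **It decides who is retested when progesterone is below 3 ng/mL.** A follicle of at least 14 mm leads to a repeat test, whereas no follicular development or corpus luteum leads to a same-day start of the next cycle (4.1, 4.2). Under 7.3, a woman with a value between 1.5 and 3.0 and a "corpus luteum on ultrasound will return for a repeat progesterone level assessment in 2-3 days".

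The visit that includes the scan also includes log review, a medication count and possible dispensing (4.2). Ultrasound results reach REDCap by abstraction from the medical record (section 14). No masked reader, central read, second read or reading standard is described.

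**The concern.** Lining thickness, lining pattern and corpora lutea number depend on the operator's reading. The plan states in advance what it expects for two of them, and the background section treats possible lining thinning under the combination as something to be ruled out. A reader who knows the arm could lean toward the expected answer or toward the feared one. Section 12.2 tests for a difference, so readings pulled together would give a non-significant result that looks like confirmation of similarity.

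The same reading controls who gets a second progesterone. An arm-linked difference in calling a 14 mm follicle or a corpus luteum would change how many women in each arm can appear in the delayed-ovulation rate. It would also change when the next cycle starts, which bears on time to pregnancy. Open treatment does not require open measurement, so this risk can be reduced without touching the interventions.

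**Working it through.** **1. What the documents say about the reader.** The open-trial wording in 4.1 concerns the patient. Section 5.5.1 concerns the sequence before assignment. Sections 7.3, 8.1 and 14 describe the scan and its data flow without naming who reads it or what that person knows. The finding is that masking is not described.

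**2. Route to the primary outcome.** Section 3.1.1 bases the primary analysis on the first progesterone of each cycle. A later value may replace it only if the first is judged mistimed from LH testing or symptoms; the scan is not a criterion. Ovulation on a scan-triggered repeat is reported separately. A narrow route remains, because a repeat can be substituted only if one was drawn, and the scan influences that. In 4.1, both branches of the 14 mm rule lead to a dose increase, so under that text the call mainly affects timing.

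**3. Formula.** Let b be an arm-linked shift in mean reading and SE the standard error of the difference. With two-sided alpha 0.05, the probability of rejection is

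Φ(−1.96 + d/SE) + Φ(−1.96 − d/SE),

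where d is the true difference plus b. With no true difference, d = b and the result is the false-positive rate.

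**4. Corpora lutea, taking 12.3.5 as stated (90% power for 0.3).** Implied SE = 0.3/(1.960 + 1.282) = 0.0925.

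- No true difference, b = 0.1: d/SE = 1.08, rejection about 19% instead of 5%.
- True difference 0.3 read 0.1 too small: d = 0.2, d/SE = 2.16, power about 58% instead of 90%.

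A shift of 0.1 means a net one extra or missed corpus luteum per ten scans in one arm relative to the other. No SD for corpora lutea is printed. The nearest are the follicle-count SDs (>10 mm) in 12.3.4: 0.56 for letrozole and 2.13 for the combination. With 57 and 75 ovulators (see step 5), SD 0.56 gives 86% power for 0.3 and 17% false positives at b = 0.1. SD 2.13 gives 12% and 5.8%. The 19% and 58% therefore depend on the plan's stated power.

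**5. Lining thickness.** Section 12.3.5 claims "94% power to detect a .25mm difference in midluteal endometrial thickness between the two arms" among ovulators. This implies SE = 0.25/(1.960 + 1.555) = 0.071 mm. Assume ovulation of 61.7% on letrozole (the five-cycle figure in the background section) and 20 points more on the combination: 0.617 × 92 ≈ 57 and 0.817 × 92 ≈ 75 women. Then SE = SD × √(1/57 + 1/75) = 0.1757 × SD, so the stated power needs SD = 0.071/0.1757 ≈ 0.4 mm. The printed SDs are 2.2 and 3.6 mm (12.3.4) and 2.3 and 3.9 mm (Table 1 of the background); 2.2 and 3.6 pool to √((2.2² + 3.6²)/2) = 2.98.

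False-positive rate with no true difference:

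| SD (mm) | SE (mm) | b = 0.25 mm | b = 0.5 mm | b = 1.0 mm |
|---|---|---|---|---|
| 2.2 | 0.387 | 9.9% | 25% | 73% |
| 2.98 | 0.524 | 7.6% | 16% | 48% |
| 3.9 | 0.685 | 6.5% | 11% | 31% |

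The b = 0.25 column is also the power for a true 0.25 mm difference, so the 94% does not reproduce. Even with all 92 women per arm and SD 2.2 it is 12%. Varying letrozole ovulation from 60% to 70% moves the b = 0.25 column only to 6.5-10.5%.

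**The case against.** The strongest reply is that the plan is silent about the reader, and silence does not show that readers know the arm. That stands: a reader might infer from the word open that scans are read unmasked, but the quoted sentence is about patients and no section says so. What keeps the point alive is that nothing withholds the arm, and the visit's other steps and the participant herself can reveal it.

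It can also be said that the endpoint that matters is a laboratory value, fixed at the first draw. This largely stands (step 2). A reader might infer that unmasked scans give one arm extra chances at the primary outcome. Section 3.1.1 does not support that beyond the narrow substitution route.

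Third, only drift that differs by arm biases the comparison; with 1:1 randomisation stratified by site, drift common to both arms largely cancels. This stands too. A 0.25 mm mean shift is not a small slip: if readings were rounded to 0.5 mm (an assumption), half of one arm's scans would have to move one step in the same direction while the other arm's did not (0.5 × 0.5 = 0.25). The direction of any drift cannot be predicted.

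Finally, masking is hard in clinics where the treating clinician scans. That limits how complete the remedy can be; it is no reason to leave reader status unrecorded.

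**Conclusion.** The concern holds as a gap in protecting the scan-based secondary outcomes, the delayed-ovulation rate and the timing of the next cycle. It does not hold as a threat of any size to the primary comparison.

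The size differs by outcome. Corpora lutea number is the more exposed: an arm-linked shift of 0.1 takes false positives from 5% to about 19%, or power from 90% to about 58%, on the assumption that the 90% in 12.3.5 is right. For lining thickness at the printed SDs, 0.25 mm takes false positives only to about 6.5-10%, and 0.5 to 1 mm is needed for a large effect. These lining figures assume 57 and 75 ovulators and that the pilot SDs carry over to the mid-luteal scan.

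Taking the stated 94% power at face value, one might infer that a 0.25 mm drift would produce a false lining difference 94% of the time. The documents' own SDs do not support that reading; the unreproduced power figure is a separate matter for the sponsor to explain.

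This is a worthwhile, inexpensive improvement rather than a defect that undermines the trial.

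**What to change.** Add to 4.1 and 8.1, in substance: where existing clinic staffing allows, the person scanning is not told the assignment; the scan request and the ultrasound form carry no arm; participants are asked not to disclose it; follicle size, corpora lutea count, lining thickness and lining pattern are recorded and locked before the log review, pill count, dispensing or opening of treatment records; and each scan form records whether the reader knew the arm.

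Report the proportion of masked scans by arm and site. Treat any analysis limited to masked scans as supportive only, because those scans will be a non-random subset, probably tied to site or clinician. If readers are already masked, one sentence saying so, together with the reader-status field, is enough.

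**Cost.** A change to the request and the form, an instruction to sites and a small adjustment to the order of visit steps. No added staff are needed if it applies only where staffing already permits. A REDCap setting alone would not suffice, since results are abstracted from the medical record. Masking will be incomplete where the treating clinician scans, the record shows the medication or the participant reveals her arm; recording reader status makes that remaining risk visible.

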4.1.1 Rationale for dosing approach

The dosing approach has been designed to escalate the letrozole dosing in subsequent cycle if participants do not ovulate. Since aromatase inhibitors are the first line agent for women with PCOS we elected to first study the increase in this compared to the combination of letrozole and CC. Consideration was given to varying doses of CC as well, however, results would be challenging to interpret with two varying doses and would not be clear if it was the increase of one medication or another that impacted ovulatory rate. By keeping CC dose constant, we can assess the standard treatment of letrozole compared to the standard treatment with CC addition at constant dose.

Stair step approach was also selected since we will be assessing progesterone and follicular status on ultrasound during luteal phase. Stair step approach will keep patient treatment progressing rather than waiting for menses or inducing menses with progestin which, both which delay the next treatment cycle.

4.2 Study Summary

Pre-screen: If patient is interested in hearing about the study, initial pre-screen will be performed to confirm basic eligibility criteria. If general eligibility criteria is met, screening visit will be scheduled or initiated. This may be part of the Screening visit/period.

Screening visit/period:

- 1. Study staff review pre-screening questionnaire
- 2. Review and obtain informed consent
- 3. Confirm eligibility criteria Inclusion/Exclusion criteria (RedCap Form)
- 4. Confirm documentation/abstract from medical record (RedCap form provided):
 - a. Demographics, medical history
 - b. Physical exam: vital signs, height, weight and BMI, hirsutism assessment
 - c. Transvaginal ultrasound
 - d. Assessment of other infertility factors: tubal and uterine factor, male factor, severe endometriosis
 - e. Inclusion laboratory testing
- 5. Pre-conception counseling: weight loss (BMI >30), tobacco cessation, folic acid use, rubella/varicella documentation, genetic carrier screening options
- 6. If progestin withdrawal bleed necessary, progestin prescription provided and will be instructed when to take it.
 - a. Progestin withdrawal bleed left to discretion of the provider
 - b. Progestin withdrawal induced if no menses greater than 3 months

Baseline visit/Randomization visit:

Baseline visit will be scheduled during cycle day 1-3 (can go up to cycle day 5) following spontaneous menses or following progestin withdraw bleed. Visit can also be a random start if anovulatory progesterone and no follicular development on ultrasound.

- 1. Urine pregnancy test
- 2. Randomization once negative pregnancy test (no follicular development and anovulatory progesterone in cases for random start)
- 3. Dispense study medication
- 4. Review medication directions (handout provided) and journal log instructions (encourage online, paper is an option)
- 5. Completion of baseline questionnaires (GAD-7, PHQ9, Ferti-QoL, and Perceived Stress Scale) or instructions provided on how to complete online
- 6. Confirm completion and obtain information if needed for RedCap Baseline Abstraction form

Monthly Midluteal visit (18 to 26 days following initiation of medication), up to 3 midluteal visits. Timing will be based on LH testing, ideally around 7-8 days post-positive test and if no positive test, CD 20-24.

- 1. Transvaginal ultrasound
- 2. Progesterone lab draw
- 3. Dispense home urine pregnancy test
- 4. Collect and review journal logs (side effects, menstrual logs, intercourse log, concomitant medications, completion or missing entry)
- 5. Count medication and confirm contact method for informing participant of plan based on lab and pregnancy test at end of cycle.
- 6. Medication dispensed for next cycle or patient may return on CD1-3 (preferable if able).

Instructions based on progesterone level and ultrasound results:

- Progesterone level ≥ 3 ng/mL → instruct participant to await menses and perform pregnancy test with menses or if no menses, perform pregnancy test 2 weeks after midluteal visit.
- 2. Anovulatory progesterone level < 3 ng/mL and with evidence of follicular development (mean follicle size ≥ 14 mm → repeat progesterone level in 10-14 days.
 - a. If repeat (2nd P4) is ovulatory progesterone level ≥ 3 ng/mL → increase treatment dose next cycle with menses after negative pregnancy test
 - b. If repeat (2nd P4) is anovulatory progesterone level < 3 ng/mL → increase treatment dose and initiate next cycle after negative pregnancy test.
- 3. Anovulatory progesterone level < 3 ng/mL and no evidence of follicular development or corpora lutea → increase ovulation medication on that that day after negative pregnancy test. This is considered the start of a new cycle. Next mid-luteal clinic visit would be scheduled for 7-8 days following positive LH test or 18 to 26 days following initiation of medication.

Menses check in appointment (via RedCap)

This check in is necessary in order to initiate next cycle. At onset of menses, each participant will take a home pregnancy test and complete the RedCap form indicating "Negative Pregnancy test". If no menses within 2 weeks after the midluteal visit, participants will take a pregnancy test.

- If positive urine pregnancy test, lab visit scheduled for serum hCG level and repeat in 48-72 hours.
- o If negative urine pregnancy test, start medication on Cycle day 3 of menses
- Submit journal logs via email or in person

Pregnancy lab Visits (part of standard of care)

- If positive urine pregnancy test, lab visit scheduled for serum quantitative hCG level and repeat in 48-72 hours.
- Appropriate rise:
 - 2 day rise multiply level x 1.7
 - o 3 day rise multiple level x 2.3
 - 4 day rise multiply level x 2.89
- If appropriate rise, schedule Transvaginal ultrasound at 6 to 7 weeks and visit with provider.
- If inappropriate rise, schedule early ultrasound (no earlier than 5 4/7 weeks) to confirm IUP and then follow up ultrasound based on initial ultrasound results. Timing of scan can be based on local protocol.
 - At UW, a 5 week ultrasound will be scheduled to confirm IUP and then follow up ultrasound based on initial ultrasound results

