7.2 Enrollment/Baseline

The enrollment/baseline visit will be scheduled when participants are on Cycle day 1-3 of their cycle or when ready to begin taking medication after pregnancy and recent/imminent ovulation have been excluded. All participants must have a negative urine pregnancy test prior to randomization.

Enrollment/Baseline Visit (Cycle Day 1-3 or at random as noted above)

- Obtain and document consent from subject on study consent form.
- Verify inclusion/exclusion criteria.
- Obtain a urine pregnancy test and confirm negative result.
 - Participation will be concluded at this point for participants with a positive urine pregnancy test; however, if a miscarriage results, participants can continue participation
- Review medical history and record in participants record in RedCap
- Assign participant ID
 - Participants IDs are assigned sequentially by site, with a 5 digit ID comprised of two components:
 - The first 2 digits of the ID are assigned based on the participant's primary study site:

Iowa City: 01

Quad Cities: 02

University of Wisconsin: 03

• Des Moines: 04

- The final 3 digits of the ID are assigned based on where the participant falls sequentially in enrollment at that site.
 - Ex. The first participant at lowa city would be 01001, the second at this site 01002, the third 01003 etc.
 - The next sequential number for the site can be identified by viewing the "Participants enrolled" report in RedCap and filtering on the participant's primary site. The assigned number should follow the final number on the report for that sites sequence.
- Randomize participant in RedCAP to determine treatment allocation

- Dispense study medication for initial cycle
- Review instructions on how to complete the calendar log and how to take study medication
 - Participants should complete the calendar log to document sexual activity, side effects, and LH surge beginning the first day they take the study medication. Calendar logs are available on RedCAP and weekly links for the calendar log will be sent to the participant's email after randomization. Subjects who do not wish to complete the calendar log electronically will have the option of completing on paper and returning to study staff at their next visit.

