 - Participants should take the study medication on cycle day 3 through 7 for a total of 5 days. If participants are unable to begin the medication on cycle day 3, they may begin on cycle day 4 or 5, but should begin medication no later than cycle day 5. Participants who meet criteria for random start will take the medication for 5 days at random start, with the first day of medication considered cycle day 3.
- Have participant complete baseline questionnaires (GAD7, PHQ9, FertiQoL, and Perceived Stress Scale, or if participant prefers to complete online, provide instructions on completing forms after visit
- Obtain a consent to obtain medical information from the participant if medical records will need to be obtained from an external provider for either fertility treatment chart abstraction and/or for potential future pregnancy chart abstraction

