7.5 Final Study Visit/Cycle 3 Menses check in

An end of treatment visit or phone call will occur after menses occurs with a negative pregnancy test or negative pregnancy test in the case of an anovulatory treatment cycle or following a positive pregnancy test. This visit will be held within 1 week of outcome (negative or positive pregnancy test) Any unused study medication will be returned to the

study team at this visit. Participants who completed paper journal logs will submit any remaining journal logs at this visit, and the end of treatment questionnaire will be completed.

Final Study Visit

- Record adverse events as reported by subject or observed by investigator.
- Record results of home urine pregnancy test and subsequent serum hCG tests.
- Review subject calendar log and record adverse events as reported by subject or observed by investigator.
- Collect any unused study medication and document participant compliance in RedCap
- Complete end of treatment questionnaire with subjects if they have not completed online
- Complete post questionnaires (PHQ9, GAD7, and Perceived Stress Scale) with participant if they have not completed online
- Provide final instructions to subject

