12.3.2 Statistical Analyses

12.3.3 Other Secondary Analyses

Generalized estimating equations will be used as appropriate for secondary analyses of differences in means and binary outcomes where the main independent variables will be treatment group, time, and their interaction, in order to account for

within-subject variability in repeated observations over time. Potential covariates in the models include recruitment site, prior exposure to the medication, use of insulin sensitizers (metformin), baseline value of the outcome, and age.

Cox proportional hazards models and Kaplan-Meier method will be used to compare the time to pregnancy between groups.

In addition to the primary intent-to-treat analysis, a per protocol analysis will be performed as a secondary analysis.

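### The baseline mood, stress and fertility quality-of-life forms are completed after open-label allocation, and FertiQoL is named again only for women with ongoing pregnancies

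*Combined protocol and SAP*

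**What the plan says.** Section 4.2 (Study Summary) numbers the steps of the baseline visit. Step 1 is the urine pregnancy test, step 2 is randomisation, step 3 is "Dispense study medication", step 4 is a review of medication directions and journal instructions, and step 5 is "Completion of baseline questionnaires (GAD-7, PHQ9, Ferti-QoL, and Perceived Stress Scale) or instructions provided on how to complete online". Step 6 asks staff to confirm completion and fill gaps, but it refers to the baseline abstraction form and sets no deadline for the questionnaires.

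Section 7.2 (Enrollment/Baseline) lists the same sequence: "Randomize participant in RedCAP to determine treatment allocation", then dispensing, then instructions on the log and medication, then the four questionnaires. For the last item it adds that "if participant prefers to complete online, provide instructions on completing forms after visit".

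Section 4.1 states the open-label condition: "Patient will be aware of the treatment intervention they are receiving".

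At the end of treatment, section 7.5 asks staff to "Complete post questionnaires (PHQ9, GAD7, and Perceived Stress Scale) with participant if they have not completed online". FertiQoL is not in that list. Section 7.4 names all four scales at the postpartum follow-up, which is reached by women with ongoing pregnancies. Appendix A has no row for the baseline scales and only a generic follow-up questionnaire row.

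On analysis, section 12.3.3 plans generalized estimating equations where appropriate for secondary outcomes, with potential covariates that include "baseline value of the outcome, and age". Neither section 3.2 nor section 12 names any of the four scales.

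**The concern.** A baseline is useful in a randomised comparison because allocation cannot have influenced it. These are self-reported measures of anxiety, depression, stress and fertility quality of life. A woman who has just learned which arm she is in, and has been handed the medication, may answer differently because of it. If that reaction differs between arms, the recorded baseline carries part of the arm difference, and subtracting it or adjusting for it distorts the later comparison. A pre-allocation value that was never collected cannot be recovered in analysis.

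FertiQoL raises a second problem. If its only named repeat is in women with ongoing pregnancies, a follow-up comparison is made in a subgroup selected by something treatment may change. Such a comparison no longer has the protection of randomisation.

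**Working it through.** The plan gives no figure to reproduce. The point rests on the order and content of visit procedures, so the sections are set side by side. The arithmetic only illustrates size.

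**Order of steps**

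| Item | Section 4.2 (numbered) | Section 7.2 (bulleted) |
|---|---|---|
| Pregnancy test | step 1 | before randomisation |
| Randomisation | step 2 | next of these items |
| Dispensing | step 3 | directly after randomisation |
| Instructions | step 4 | after dispensing |
| Four questionnaires | step 5, or online | after instructions, or online after the visit |

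The bullets in 7.2 are not numbered, but their order matches 4.2, so the sequence is not a slip in one place. Neither section requires the forms to be finished before allocation is known or before the first dose.

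**Could a form be completed on drug?** The visit may fall on cycle day 1 to 3 (up to day 5). Dosing runs on days 3 to 7, with a start on day 4 or 5 allowed, or begins at random start. A woman seen on day 3 to 5, or at random start, could therefore begin treatment at once and complete the online form during the five dosing days. The documents do not allow that share to be estimated.

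**Effect on an analysis that used these baselines.** Let *s* be the arm difference in the recorded baseline that allocation itself caused, in SD units, and *b* the slope of the follow-up score on the baseline score.

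- Change score: bias = −*s*
- Baseline-adjusted comparison: bias = −*b* × *s*

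With assumed *s* of 0.1 to 0.3 and assumed *b* of 0.3 to 0.7 (neither is in the documents):

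- Change score: 0.1 to 0.3 SD in size
- Adjusted, smallest: 0.3 × 0.1 = 0.03 SD
- Adjusted, largest: 0.7 × 0.3 = 0.21 SD

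**FertiQoL follow-up.** Schedule as written: baseline, yes; final study visit, not named; postpartum contact, yes, for ongoing pregnancies. With 184 randomised (section 12.1.4) and an assumed proportion *p* reaching the postpartum contact, the number without a repeat is 184 × (1 − *p*):

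- *p* = 0.20: 184 × 0.80 = 147.2, about 147
- *p* = 0.275: 184 × 0.725 = 133.4, about 133
- *p* = 0.40: 184 × 0.60 = 110.4, about 110

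The middle value borrows the letrozole live birth proportion over five cycles in the earlier trial (section 12.1.1). This trial has up to three cycles and a combination arm, so that value is a reference point within the range and not a bound.

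**The case against.** The strongest reply is that no planned analysis is harmed. The four scales appear only in visit procedures. The plan specifies no change score, baseline adjustment or between-arm test for them. The covariate list in section 12.3.3 is generic and only potential, so a reader who infers that the plan commits to adjusting these scales for a contaminated baseline goes further than the text. This stands, and it limits the harm to an analysis that the plan permits but does not name.

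Other stronger readings also fail:

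- **That all 184 baselines are taken on drug.** Completion at the visit is offered, and online completion is for those who prefer it. Knowledge of the arm can affect everyone who follows the listed order. Drug exposure can affect only an unknown subset.
- **That the drugs' listed risks prove contamination that differs by arm.** Section 2.2.1 lists mood changes for clomiphene and not for letrozole. That makes a difference conceivable, but a risk list is not comparative evidence of an effect within days of the first dose.
- **That 27.5% caps the share with a second FertiQoL.** The plan hypothesises a higher live birth rate with the combination, and postpartum follow-up is defined by ongoing pregnancy, not by live birth.
- **That FertiQoL certainly has no end-of-treatment value.** Section 7.5 mentions a separate end-of-treatment questionnaire without giving its content. FertiQoL is not named in it, and that is as far as the text goes.

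It is also fair to object that making the forms a hard condition for randomisation would be disproportionate in a visit window of a few days. The fix does not ask for that.

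What the reply does not answer is that the protocol asks every woman for these forms and calls them baseline, while scheduling them where they cannot reliably serve as one.

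**Conclusion.** The point holds, with limited consequence. Both descriptions of the visit put the questionnaires after open-label randomisation and dispensing, with no deadline for online completion. As scheduled, women answer knowing their arm, and some may already have started treatment. FertiQoL is not named at the final study visit, so its only named follow-up is in a group defined after randomisation. About 110 to 147 of 184 women would lack a repeat if 20% to 40% reached the postpartum contact, which is an assumption.

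The harm is confined to a between-arm change-from-baseline or baseline-adjusted analysis of these four scales, such as the generic model in section 12.3.3. The bias of 0.03 to 0.21 SD in an adjusted comparison rests wholly on assumed shifts and slopes. The primary ovulation outcome, the secondary outcomes listed in section 3.2 and the sample size are untouched, and a reader should not infer otherwise. The change is still worth making, because it costs little and a missing pre-allocation value cannot be recovered later.

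**What to change.** In sections 4.2 and 7.2, move the four questionnaires, on site or online, ahead of the randomisation step. Record the completion date of each form. State that a form dated after randomisation will not be used as a baseline covariate or in a change score. Do not make completion a hard condition for randomisation: a woman without a completed form can still be randomised within the visit window.

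In section 7.5, add FertiQoL to the questionnaires at the final study visit for all women. That visit follows either a negative or a positive pregnancy test, so it does not select on pregnancy. Showing the scales in Appendix A would keep the schedule consistent with the text.

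The cost is a reordered list, a recorded date, a few minutes before randomisation and one more existing form at the final visit. Treatment and sample size do not change. Some late forms will be lost as baselines, which is the price of keeping the rest free of allocation effects.
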